**Figure 7-5      Meta-analysis of angioedema incidence rates up to 1 year after exposure to ACEI**

Meta-analysis of angioedema incidence rates up to 1 year

Source data from: [Burkhart et al \(1996\)](#), [Miller et al \(2008\)](#), [Toh et al \(2012\)](#)

[figure not shown]

## 7.6 Data management

### 7.6.1 Data collection and processing

Data collection and processing will be done locally according to a common data model, while pooling of aggregated data in a meta-analysis will be done at PHARMO (see [Figure 7-6](#) for overview).

**Figure 7-6 Model for data sharing and processing**

A distributed common data model approach will be used to analyze data in an efficient manner. Each database extracts study specific data locally and transforms them into a simple common data model that has the same structure across all sites, i.e., standardized patient, medication, diagnosis, and assessment files, linkable via a patient unique identifier (see [Figure 7-5](#)), as defined in a data dictionary. Based on the relevant diagnostic codes and key words (for free text search in the PHARMO GP Database only), a data processing algorithm will be constructed for each safety event based on the consensus of the data partners, and lead to potential safety events

in the input files. The required variables have been defined by the coordinating center and are captured in a data dictionary with instructions, which is sent to the participating partners. To verify extractions and transformations, a quality check script is sent to the data partners. The output is shared with the coordinating center and compared to other sites, and subsequently discussed with the sites, who then can update the data if errors are detected. This process is repeated until quality is sufficient.

Validation of the safety event angioedema and algorithms is ongoing, and is planned to be finalized end of Q1 2022, i.e. before the final LCZ696B2014 study report (due Q4 2022).

### 7.6.2 Programming

All programming for local data transformation of the input files into relevant evidence for the study objectives is created in SAS by PHARMO. At Aarhus, HSD, PHARMO, SIDIAP, CPRD, and GePaRD SAS version 9.4 or higher (SAS Institute Inc., Cary, North Carolina) are used for data extraction and transformation. At ARS, R (R Foundation for Statistical Computing, Vienna, Austria) is used for data transformation (since ARS does not have a SAS license). ARS will create the data transformation program in R, based on the SAS script that is supplied by PHARMO. Using a simulated dataset, the comparability of the SAS and R programs is verified. The SAS or R programs will be run locally by the data partners against the common data model to generate the analytical datasets on individual level.

Due to the different database characteristics and coding schemes it is not possible to use one single data extraction algorithm for all of the databases. To reconcile differences across terminologies, a shared semantic foundation will be built for the definitions of safety events by selecting diagnostic codes, matching the mapping terms listed in [Table 12-1](#), and setting up a multi-step and iterative process for the harmonization of safety event data ([Trifiro et al 2014](#)). The sequential steps of this process are shortly described below:

All safety events, risk factors, or potential confounders, will be ascertained using a list of agreed ICD-9/-10 CM (Denmark, Italy, the Netherlands, and Spain), ICD-10 GM (Germany), ICPC (the Netherlands), WCIA (the Netherlands), and READ (UK) codes. The proposed lists of codes will be created following a number of steps:

- Case definition of the safety events of interest (e.g. angioedema)
- Preliminary list of concept identifiers by searching web-based lists of ICD-9/-10 CM, ICD-10 GM, ICPC, and WCIA codes and descriptions, and mapping READ codes to the ICD codes;
- Addition of codes found after literature review of validated lists of codes for each of the safety event of interest in each of the databases;
- In addition, for the PHARMO GP Database, where free text is available and ICPC coding is not mandatory and often insufficiently granular to find specific diagnoses, the labels of the codes are considered for free text search of the safety events.
- Consensus with partners involved in the management and analysis of each of the databases, thereby data sources. As coding might change over time, relevant codes might be updated during the course of the project. Harmonization and operationalization of these

code lists will take place between databases by comparison of population-based age and sex standardized IRs, according to standard quality assurance procedures (see below).

### **Definition of data extraction algorithm**

Based on the relevant diagnostic codes and key words (for free text search), a data extraction algorithm will be constructed for each safety event based on the consensus of the data partners. This data extraction algorithm will then be implemented by all data partners.

### **Event data extraction**

Subsequently, each data partner extracts data locally and transforms them into a simple common data model, i.e. standardized patient, drug, and event files linkable via a patient unique identifier.

### **Benchmarking of incidence rates of events**

For each safety event of interest and covariate we benchmark database specific IRs and frequencies for the covariates, using SAS and R scripts in a quality run. The observed IRs are compared to IRs estimated from previous database studies and literature. Outliers are identified and further investigated in an iterative manner.

This multi-step process was used successfully in several other European multi-database projects ([Trifiro et al 2014](#)). It maximizes the involvement of data partners in the study by utilizing their knowledge on the characteristics and the process underlying the data collection. After completion of harmonization, output tables for calculation, and analysis of safety events of interest will be created by the local data processors.

The difference in incidence of angioedema using only data from GP systems and the incidence of angioedema obtained from also secondary care data will be investigated.

### **Data elaboration**

A standardized SAS script and instructions will be created by the PHARMO Institute for Drug Outcomes Research, using SAS (version 9.4). ARS will recreate the scripts in R and outcome tables will be compared.

#### **7.6.3 Missing data**

Since the underlying data represent attended medical care, we generally assume that absence of information of clinical events means absence of that condition. Life-style data, e.g. BMI and smoking, are in particular opportunistically recorded. If data on such factors are missing, this occurs generally 'not at random' but lack of data may indicate that recording of these factors is of no direct clinical importance. For that reason, no imputation will be done for missing data. Instead, missing data will be summarized in a separate category and the missing-indicator method will be used. Lack of information on risk factors such as smoking, or the use of certain drugs may occur, but this is unlikely differential. Information on race is only available in CPRD. Since this information is lacking in a large proportion of the data and the proportion of black patients (relevant to the safety event of angioedema) is available in <0.5% of patients, race will be reported descriptively and will not impact the analyses.

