*Ad objective 2:* The potential gap in sacubitril/valsartan prescriptions (or pharmacy fills) due to specialist prescribing in or outside the hospital was assessed by the number of patients with a hospitalization or referral to a specialist in the 3 months prior to the index date. A substantial proportion of sacubitril/valsartan users included in the feasibility study cohort were in specialist/ambulatory care (proportion ranged from 17% in Aarhus to 72% in HSD) or hospitalized within 3 months prior to the first sacubitril/valsartan prescription (proportion ranged from 18% in HSD to 42% in GePaRD). The time between referral or hospitalization for HF and first identified sacubitril/valsartan prescription (or pharmacy fill) in CPRD, HSD, GePaRD, and PHARMO was between 0 and 20 days for most sacubitril/valsartan users. In SIDIAP, this was more than 30 days for most patients. It seems plausible that for a number of these patients the first sacubitril/valsartan prescription may have been missed, either because inpatient prescribing is not present in all databases or outpatient specialist prescriptions are not captured (CPRD, HSD). The impact of misclassification of treatment start cannot be assessed with sensitivity analyses, because patients with an angioedema event during treatment that is not captured, will not have subsequent out-patient prescription records for sacubitril/valsartan that are captured, and therefore will not be included in the sacubitril/valsartan cohorts. If initiation of sacubitril/valsartan use is missed, but later exposure is captured, exposure time will be slightly underestimated and safety event rates may be slightly overestimated.

*Ad objective 3:* Crude and age-/sex-standardized event rates were calculated for the safety events of interest in the general (adult) database population and were compared across databases overall and by data provenance.

As an example, [Figure 7-1](#) displays the assessment of safety event rates for angioedema (*'narrow'* definition).

**Figure 7-1 Age- and sex-standardized safety event rates of angioedema (*'narrow'*) in a general adult population by provenance over time**

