### 7.3.2 Safety events of interest

The safety events of interest include a recorded diagnosis of:

- Angioedema (primary event of interest; as ‘*narrow*’ [primary analysis] and ‘*hypersensitivity reaction*’ [sensitivity analysis])
- Hypotension (as ‘*narrow*’ [primary analysis] and ‘*broad*’ [sensitivity analysis])
- Hyperkalemia
- Hepatotoxicity
- Renal impairment

as identified from in- and/or outpatient registry or claims data, or electronic medical records. Recorded abnormal laboratory values (for identification of hyperkalemia) will also be included for identification of outcomes of interest, if available (not available for ARS and GePaRD).

Safety events of interest will be identified using the event-specific codes based on the coding system(s) used in the databases of interest (e.g. READ, ICD-9/-10 CM, ICD-10 GM, or ICPC codes (see [Table 7-8](#) for details). A detailed knowledge of the healthcare systems in the different countries is necessary to provide the correct definitions for all safety events.

An initial list of terms that would be used for the event definition mapping is supplied in Annex [Section 12.3](#). Additional natural language processing (NLP) terms will be used in PHARMO to further differentiate within ICPC codes.

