**Table 7-8 Overview of databases used in the study**

Characteristics	Database						
	PHARMO	CPRD	Aarhus	HSD	ARS	SIDIAP	GePaRD
Country (population size 2019 in million inhabitants)†	Netherlands (17.1)	United Kingdom (66.8)	Denmark (5.8)	Italy (59.2)	Italy (59.2)	Spain (46.4)	Germany (82.4)
Type of database	EMR	EMR	ADM	EMR	ADM	EMR	Claims
Number of patients, millions	4.0 (approximately 1.2 million with both GP and outpatient pharmacy data available)	5.7 (approx. 55% linked to HES data)	1.5	1.5	3.6	5.1 (about 33% linked to hospital data)	20
Date in	Yes	Yes	Yes	Yes	Yes	Yes	Yes
Date out	Yes	Yes	Yes	Yes	Yes	Yes	Yes
Date of death	Yes	Yes	Yes	Yes	Yes	Yes	No
Cause of death	No	No (only available through linkage of data to the Office for National Statistics death registration data)	Yes	No	Yes	No	Yes (date of in- hospital death is available. Date of out-of-hospital death can be estimated)
Updates	Annual (October)	Yearly (May/June)	Yearly (April)	2-times a year: (30/06 and 31/12)	Every month with a lag-time of 3-4 months	Yearly (April/May)	Yearly (mid year)
Prescriptions							
Outpatient Rx	Yes	Yes (specialist incomplete)	Yes	Yes	Yes	Yes (specialist incomplete)	Yes
Coding of drugs	ATC	Gemscript codes	ATC	ATC	ATC and local Italian coding system	ATC	ATC GM

Characteristics	Database						
	PHARMO	CPRD	Aarhus	HSD	ARS	SIDIAP	GePaRD
Dosing regimen	Yes	Yes (incomplete)	No	Yes (incomplete)	No	Yes	No
Safety events of interests							
Hospitalizations	Yes	Yes (for about 55%)	Yes	Yes (if reported back by patients)	Yes	Yes (for about 33%)	Yes
Emergency visits	No	No	Yes	Yes (incomplete)	Yes	No	Yes (incomplete, only emergency visits to GPs)
Outpatient diagnoses	Yes	Yes	Yes	Yes	No	Yes	Yes (diagnoses made by GPs and diagnoses made by specialists in the outpatient setting)
Coding of disease	ICPC, ICD-10 CM	READ (ICD-10 CM for HES data)	ICD-10 CM	ICD-9 CM	ICD-9 CM	ICD-10 CM (ICD-9 CM for hospital data)	ICD-10 GM
Laboratory data	Yes	Yes	Yes	Yes	No	Yes	No (only information on date and type of test is recorded, results of tests are not available)

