#### **7.4.2 Sistema d'Informació per al Desenvolupament de la Investigació en Atenció Primària' (SIDIAP) – Spain**

GPs play an essential role in the public health care system of Spain, as they are responsible for primary health care, long-term prescriptions, and specialist and hospital referrals. The Spanish public health care system covers more than 98% of the population. The SIDIAP database comprises of electronic medical records of a representative sample of patients attended by GPs in Catalonia (North-East Spain), covering a population of more than 5.1 million patients (about 80% of the total of 7.5 million population of Catalonia) from 274 primary care practices with 3,414 participating GPs. The SIDIAP data comprises the clinical and referral events registered by primary care health professionals (GPs and nurses) and administrative staff in electronic medical records, comprehensive demographic information, community pharmacy invoicing data, specialist referrals, and primary care laboratory test results.

Linked data on hospital admissions and their major outcomes are available for 30% of the practices in SIDIAP. Health professionals gather this information using ICD-10 CM codes, and structured forms designed for the collection of variables relevant for primary care clinical management, such as country of origin, sex, age, height, weight, body mass index, tobacco and alcohol use, blood pressure measurements, blood and urine test results. Only GPs who meet quality control standards can participate in the SIDIAP database. Encoding personal and clinic identifiers ensures the confidentiality of the information in the SIDIAP database. Recent reports have shown the SIDIAP data to be useful for epidemiological research ([Garcia-Gil et al 2011](#)).

As this is a primary care database, information on specialist prescribing, drug dispensing, and actual drug intake is missing.

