## 12.3 Annex 3 – Additional information

### 12.3.1 Terms to be used for mapping of outcomes

**Table 12-1 Terms to be used to identify cases with the outcomes of interest**

Outcome of interest	Terms to be used	Comments
Angioedema	ICD-9/-10CM/ICD-10GM/Read/ICPC codes corresponding to angioedema, angioneurotic edema, Quincke edema, or any other synonym Allergic oedema, Anaphylactic reaction, Anaphylactic shock, Anaphylactoid reaction, Anaphylactoid shock, Angioedema, Bronchial oedema, Circumoral oedema, Endotracheal intubation, Epiglottic oedema, Gastrointestinal oedema, Genital swelling, Gleich's syndrome, Intestinal angioedema, Laryngeal dyspnoea, Laryngeal obstruction, Laryngospasm, Laryngotracheal oedema, Genital oedema, Mouth oedema, Oropharyngeal spasm, Palatal oedema, Penile oedema, Penile oedema, Periorbital oedema, Pharyngeal oedema, Reversible airway obstruction, Scrotal oedema, Scrotal swelling, Skin oedema, Swelling face, Swollen tongue, Tongue oedema, Tracheal obstruction, Tracheal oedema, Upper airway obstruction, Vaginal oedema, Visceral oedema, Vulval oedema, Vulvovaginal swelling	Primary analysis (' narrow ' definition)  Sensitivity analysis including additional terms on top of the above (' broad ' definition)  Specifically excluded [because too unspecific, risk of too many false positives]: Endotracheal intubation, Reversible airway obstruction, Skin oedema, Upper airway obstruction  'Endotracheal intubation' to be used however, in the context of assessing severity of angioedema (if available/feasible)
Hypotension	Hypotension, Blood pressure decreased, Orthostatic hypotension, Dizziness, Postural dizziness, Presyncope, Syncope	Specifically excluded [because too unspecific, risk of too many false positives]: Depressed level of consciousness, Loss of consciousness  No BP measurements to be included to identify cases of hypotension  Sensitivity analysis for syncope (as a proxy for severe hypotension)
Hyperkalemia	Hyperkalemia, Blood potassium increased	Include lab values for potassium measurements; definition: K + >5.4 nmol/l
Hepatotoxicity	Acute hepatic failure, Drug-induced liver injury, Hepatic failure, Hepatic necrosis, Acute hepatitis, Fulminant hepatitis, Toxic hepatitis, Hepatocellular injury, Hepatorenal failure, Hepatotoxicity, Liver injury, Hepatic encephalopathy	--

---

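### In the five databases with potassium results, hyperkalaemia rates count only detected events, so they depend on recorded testing, and they are pooled with code-only rates from the other two

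*Protocol*

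**What the plan says.** - **Missing data (Protocol Section 7.6.3).** The rule is that "we generally assume that absence of information of clinical events means absence of that condition", and "no imputation will be done for missing data". No exception is made for an event that only a laboratory test can show.
- **Outcome (Section 7.3.2).** "Recorded abnormal laboratory values (for identification of hyperkalemia) will also be included for identification of outcomes of interest, if available"; these are "not available for ARS and GePaRD". Table 7-5 marks potassium results as used in PHARMO, HSD, Aarhus, CPRD and SIDIAP. Table 12-1 repeats the instruction: "Include lab values for potassium measurements".
- **Time at risk (Sections 7.2.6 and 7.7.1.2.2).** Follow-up runs from cohort entry to the event or censoring. The rate is events over person-time, by database and pooled. Neither depends on a test having been done.
- **Comparison.** The aim in the Abstract names hyperkalaemia among the risks set against ACEI use. The planned adjusted relative risks concern angioedema only (Abstract, Data analysis; Section 7.7.1.2.2).
- **What the laboratory data cover.** SIDIAP holds "specialist referrals, and primary care laboratory test results" (Section 7.4.2). Of the three PHARMO databases to be used, only the GP database is described as holding laboratory results (Section 7.4.5). For GePaRD, Table 7-8 notes that "only information on date and type of test is recorded".

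**The concern.** Reading silence as absence is reasonable for an event that brings a patient to care and is then coded. A raised potassium is different, because without a test nobody knows the value. Where potassium results are a case-finding route, the numerator depends on testing and the denominator does not.

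Two outputs are affected. The first is the absolute rate in each of the five databases, which is a primary-objective result for an identified risk in the risk management plan. The second is the pooled rate, which mixes code-plus-laboratory rates with code-only rates. There is also a conditional third: if sacubitril/valsartan starters and ACEI users are tested at different frequencies, a difference between cohorts 1-2 and 3-4, or the lack of one, cannot be separated from a difference in testing.

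The protocol treats the neighbouring outcomes differently. Sections 7.3.2.4 and 7.3.2.5 drop laboratory values for hepatotoxicity and renal impairment, partly because some databases lack them. The same gap exists for potassium, yet the results are kept and no check on testing is attached.

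**Working it through.** **The plan's own figure.** The only study-size figure concerns angioedema: 132 / 24,000 = 5.5 per 1,000 patient-years. The exact Poisson interval is 4.60 to 6.52, which agrees with the stated 4.6 to 6.5. It is not in dispute, and no counterpart is given for hyperkalaemia.

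**Does the laboratory route matter?** Section 5.3 gives, for the pivotal trial, potassium above 5.4 mmol/l against reported hyperkalaemia:
- sacubitril/valsartan: 19.7% / 11.6% = 1.70
- enalapril: 21.1% / 14.0% = 1.51

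A reported adverse event is not the same as a routine diagnosis code, so this is only an indication. It suggests that code-only and laboratory-supplemented rates can differ a good deal. (The potassium cut-off also differs between Section 7.3.2.3 and Table 12-1, and the two must be reconciled.)

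**How testing enters the rate.** Let p be the probability that a patient with a true event has a recorded result that shows it, and c the share of events coded whether or not a result is recorded. Then:
- share of true events detected = c + (1 − c)p
- factor applied to the true ratio between two cohorts = [c + (1 − c)p₁] / [c + (1 − c)p₂]

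The documents give neither p nor c. I take p from 50% to 90%, and c = 0 or 0.5.

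*Absolute rate.* With c = 0, between 50% and 90% of events are detected. With c = 0.5, the range is 0.5 + 0.5 × 0.5 = 75% to 0.5 + 0.5 × 0.9 = 95%.

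*Ratio between cohorts when the true risks are equal:*

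| Tested, sacubitril/valsartan v ACEI | c = 0 | c = 0.5 |
|---|---|---|
| 80% v 70% | 0.80/0.70 = 1.14 | 0.90/0.85 = 1.06 |
| 90% v 60% | 0.90/0.60 = 1.50 | 0.95/0.80 = 1.19 |
| 70% v 90% | 0.70/0.90 = 0.78 | 0.85/0.95 = 0.89 |

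For scale, Section 5.3 cites a meta-analytic risk ratio for hyperkalaemia against ACEIs of 1.16 (0.88 to 1.54). In the trial, the laboratory-based ratio was 19.7/21.1 = 0.93; if every event were laboratory-found, testing 7% more frequent (relative) in starters would bring it to 1.00 (21.1/19.7 = 1.07).

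**How much reaches the pooled rate?** In the feasibility work (Section 7.1.2), GePaRD supplied 4,724 of 5,185 sacubitril/valsartan initiators, so at most 461 (8.9%) came from databases with potassium results. In the fourth interim report, the count without ARS and GePaRD was over 89,000 of almost 567,000 in cohort 3 (about 16%) and over 21,500 of over 116,000 in cohort 4 (about 19%). These are different extractions and should not be compared closely. They do show that most patients are in code-only databases. How far this dilutes the pooled rate depends on the pooling weights, which are left to the SAP.

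**Is it handled elsewhere in the protocol?** The linkage strata in Section 7.7.1.2.2 add hospital diagnoses, not tests. The GP versus secondary-care check in Section 7.6.2 and the false-negative rate in Section 7.7.1.2.3 are for angioedema. Validating recorded events cannot find patients who were never tested.

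**The case against.** The strongest reply has four parts.

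1. *Counting recorded events over person-time is the usual design in such databases, and Section 7.6.3 says only that the rule holds generally.* This stands as a defence of the design. It does not make an untested patient known to be free of hyperkalaemia, and the protocol nowhere says so.
2. *No comparison of hyperkalaemia is planned.* This stands. A reader might infer that a biased hyperkalaemia contrast is built into the plan; it is not. What remains is the absolute rates, their pooling, and the informal reading across cohorts that the stated aim invites.
3. *Unequal testing is not shown.* This also stands. Section 7.1.2 reports that "A substantial proportion of sacubitril/valsartan users included in the feasibility study cohort were in specialist/ambulatory care" (17% to 72%), and that 18% to 42% had been in hospital, in the three months before first prescription. A reader might infer that starters are tested more, or that their specialist tests go unseen. The passage supports neither: it covers only sacubitril/valsartan users, before the index date, describes care setting and not tests, and gives no ACEI figure. The 42% is from GePaRD, which supplies no results.
4. *Sensitivity analyses for event misclassification are left to the SAP (Section 7.7.1.2.3).* The SAP may already contain what is asked for, and its absence here is no finding. The point is that Section 7.6.3 fixes a general reading of missing records that does not suit this outcome.

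**Conclusion.** The point holds in limited form. In PHARMO, HSD, Aarhus, CPRD and SIDIAP, the planned hyperkalaemia rates are rates of detected events and undercount true events by an amount that depends on testing. They are not like-for-like with the ARS and GePaRD rates. Both statements follow from the protocol text and need no assumption about how cohorts differ.

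Confounding of a side-by-side reading by testing is conditional on testing being unequal, and neither its size nor its direction can be known from the documents. The illustrative ratios, 0.78 to 1.50 if every event is laboratory-found and 0.89 to 1.19 if half are coded regardless, rest on my assumed testing probabilities. They apply to the five laboratory databases and not to the pooled rate, where most patients contribute code-only data. The angioedema analyses are untouched.

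**What to change.** - **Section 7.6.3:** state that absence of a potassium result is not evidence of no hyperkalaemia, so laboratory-supplemented rates are rates of detected events.
- **Section 7.7.1.2.2, testing:** report by cohort and database the share of patients with any recorded potassium result and the tests per patient-year. For GePaRD, use the test dates and types it holds. The extraction must include all potassium results and not only abnormal ones; the protocol does not say whether it does, so check this first.
- **Section 7.7.1.2.2, rates:** in the five laboratory databases, show code-only beside code-plus-laboratory rates. Pool the code-only rate across all seven databases as a sensitivity analysis.
- **Interpretation:** read any cohort difference in hyperkalaemia alongside the testing frequencies. Do not set a fixed cut-off, such as dismissing any difference smaller than the testing ratio: drug-related rises or symptoms can themselves prompt testing, so such a rule could hide a real effect. Events per 100 tests may be shown descriptively only, since selective testing of high-risk patients raises that figure.

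The cost is a little more tabulation, possibly a wider laboratory extraction, and a more cautiously stated hyperkalaemia result.
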